In case of CIDP, a first-line treatment consisting of 2 g/kg of body weight loading dose administered over 2-5 days followed by subsequent maintenance doses every 3 weeks were recommended by the European Federation Neurological Society [13]. In a randomized, placebocontrolled, double-blind, response-conditional crossover trial with IVIG (Gamunex), CIDP patients received a loading dose (2 g/kg of body weight) and maintenance doses (1 g/kg of body weight) every 3 weeks for up to 24 weeks (first period). Non-responder subjects were crossed over to receive the alternate treatment according to the same treatment schedule (second period) as was used in the first period. IVIG 10% showed a benefit with a significantly higher response rate in functional disability improvement versus placebo after 24 weeks of treatment (p=0.0002). Furthermore, long-term maintenance with IVIG also significantly had a reduced rate of relapse probability (13%) relative to IVIG responders who had therapy withdrawn (45%) [15].

In addition, Flebogamma[®] 5% DIF shows a suitable profile for this treatment schedule based on: 1) Flebogamma[®] 5% DIF pharmacokinetic studies in PID; 2) Flebogamma[®] 5% DIF administration with an immunomodulatory effect on other indications; 3) Flebogamma[®] 5% DIF safety profile. In a clinical study assessing safety and efficacy in PID, pharmacokinetics of Flebogamma[®] 5% DIF was assessed in 20 subjects after at least the 5th month of treatment. Pharmacokinetic analysis revealed that Flebogamma[®] 5% DIF infusions (at a dosage of 0.3 - 0.6 g/kg of body weight) had a mean estimated half-life for total IgG of approximately 31 days. Therefore, the reported half-life demonstrated that every 4 weeks infusions of Flebogamma[®] 5% DIF are suitable dosing intervals for maintenance doses.

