10.1.3 Statistical analysis of safety

The safety analyses will be addressed by listing and tabulation of AEs (includes suspected ADRs), vital signs, physical assessments and clinical laboratory tests. Data will be described using descriptive analyses.

Adverse events:

Safety analysis will be primarily focused on a descriptive analysis of suspected ADRs. Safety assessment will be based on the prevalence of suspected ADRs that occurred during the clinical trial.

Adverse events will be coded and classified using MedDRA® terms (system organ class and preferred terms).

Adverse events will be classified as treatment emergent AEs (TEAEs) or non-treatment emergent AEs (non-TEAEs) depending on the comparison of AE onset date/time with the start date/time of study treatment with the investigational product. A TEAE will be defined as an AE which occurs between the beginning of the first infusion of Flebogamma® 5% DIF or Normal Saline Solution and the final visit of the clinical trial. A non-TEAE will be defined as an AE which occurs prior to the start of study treatment. Non-TEAEs and TEAEs will be summarized separately. TEAEs that occurred during the Treatment period (from the first investigational product infusion at IV1, Week 0, to the

EoTV, Week 52) and Follow-up period (from EoTV, Week 52, to the FV, Week 76) will be collectively and separately summarized.

All AEs will be summarized by presenting subject incidences and percentages, and they will also be listed by body systems with subject identification codes.

In addition, TEAEs, including suspected ADRs, will be summarized by each treatment arm, system organ class, preferred term, causal-relationship, intensity (severity) and seriousness (serious versus non-serious) using descriptive statistics. At each level of summarization, a subject will only be counted once per system organ class or preferred term using the most severe or causal relationship AE.

AEs, including suspected ADRs, of thromboembolic and hemolytic origin will also be summarized separately.

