2 INTRODUCTION

This Statistical Analysis Plan (SAP) is based on Protocol IG1104 Version 7.0, dated March 7th, 2022.

Subsequent to the finalization of the protocol, Instituto Grifols S.A. took the decision to prematurely terminate this trial once subjects participating at the time of the decision had completed their study treatment. The early termination resulted from a business decision by Grifols, with no safety concerns regarding the Investigational Product and no changes in the risk/benefit for ongoing subjects participating in the study.

As a commitment to study participants, all subjects that were enrolled at the time of the decision were given the opportunity to complete blinded study drug infusions, continue with treatment visits and be assessed as per protocol. In addition, where feasible and consented by study subject, assessments and procedures to be performed during an early discontinuation visits were to take place after the last investigational product infusion on infusion visit 13. Alternatively, subjects in the follow-up period were to be discontinued as soon as possible.

The purpose of this SAP is to ensure that the statistical methodologies that will be used, and the data listings, summary tables and figures which will be produced, are appropriate and complete to support valid conclusions regarding the study objectives and the completion of Clinical Study Report (CSR).

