11.1 Adverse Events

Analysis of AEs will be primarily focused on a descriptive analysis of AEs, suspected adverse drug reaction (ADRs) and adverse reaction (AR). Safety assessment will be based on the prevalence of suspected ADRs and AR occurred during the clinical trial.

- Suspected ADRs are defined as AEs with a causal relationship to study treatment of "Definitely Related", "Probably Related", "Possibly Related" or "Doubtful/Unlikely Related".
- ARs are defined as AEs with a causal relationship to study treatment of "Definitely Related".

AEs will be classified according to their onset date/time into the following categories:

Treatment emergent AEs (TEAEs): AEs with an onset date/time between first study treatment date/time and final study visit date or a pre-existing AE that worsens in severity within the same time window.

TEAEs will be further classified as follows:

- o On-treatment TEAEs: TEAEs with an onset date/time between first study treatment date/time and last study treatment date +4 weeks.
- o Infusional TEAEs: TEAEs with an onset date/time between the start date/time of study treatment infusion and 72 hours post-completion of the infusion of total dose of study treatment during any of the 2-day infusion periods.
- Post-treatment TEAEs: TEAEs with an onset date/time after the last study treatment date/time +4 weeks.
- non-TEAEs: all other AEs i.e. AE which occur prior to the start of study treatment.

For the purposes of classifying AEs into the above categories, partial AE start and end dates will be imputed to allow comparison with the study treatment date start and end dates. Section 13.1.1 below presents the imputation rules. Note, the imputed dates will be used for classification purposes only and the original partial AE dates will be presented in data listings.

AEs will be coded using MedDRA dictionary version 17.1 and summarized (stage 1 and stage 2 combined) by treatment group, system organ class (SOC) and preferred term (PT) as follows:

- TEAEs:
 - On-treatment TEAEs
 - overall
 - by maximum severity
 - by maximum causal-relationship
 - **SAEs**
 - suspected ADRs
 - ARs
 - **AESIs**
 - suspected ADRs of Special Interest (SI),
 - ARs of SI

- o Post-treatment TEAEs
 - overall
 - SAEs
- Infusional TEAEs
 - overall
 - SAEs
 - suspected ADRs
- Non-TEAEs

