Adverse events will be summarized by presenting, for each treatment group, the number and percentage of patients with any AE, any AE within each SOC and any AE within each PT (grouped by SOC).

For summaries by maximum severity, if a patient reported more than one AE with the same PT, the AE with the maximum severity will be presented. If the severity of an AE is missing, the severity will be treated as missing in summaries. If a patient reported more than one AE within the same SOC, the patient will be counted only once under the maximum severity within the SOC.

Corresponding reporting rules will be applied for summaries by maximum causal-relationship.

All AEs will be listed by treatment group and subject identifier. In addition, subjects with SAEs and AEs leading to premature discontinuation of treatment period from the study will be individually listed.

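### SAP 11.1 ends the special-interest AE tables at last treatment plus 4 weeks, plans no table over both periods, and lets subjects with truncated follow-up dilute the post-treatment percentages

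*SAP*

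**What the plan says.** SAP 11.1 sorts treatment-emergent events by onset. The first window is "On-treatment TEAEs: TEAEs with an onset date/time between first study treatment date/time and last study treatment date +4 weeks". The second is "Post-treatment TEAEs: TEAEs with an onset date/time after the last study treatment date/time +4 weeks". An overlapping infusional window is also defined. Treatment emergence itself ends at the subject's final study visit.

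The table list in SAP 11.1, by SOC and preferred term with stages combined, is:

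- On-treatment: overall, maximum severity, maximum causality, SAEs, suspected ADRs, ARs, AESIs, suspected ADRs of special interest, ARs of special interest.
- Post-treatment: overall, SAEs.
- Infusional: overall, SAEs, suspected ADRs.

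The statistic is "the number and percentage of patients with any AE", and likewise within SOC and preferred term. SAP 11 bases all safety analyses on the Safety population, which SAP 5.2 defines as everyone with at least one infusion.

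Protocol 10.1.3 says of TEAEs in the treatment and follow-up periods that they "will be collectively and separately summarized", and adds: "AEs, including suspected ADRs, of thromboembolic and hemolytic origin will also be summarized separately". Protocol 9.3.7 names thromboembolic events and haemolysis as the events of special interest. SAP 12, which records changes to protocol-specified analyses, contains only the cytokine change.

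SAP 2 describes the early termination. Subjects on treatment could complete their infusions, with early-discontinuation assessments after the IV13 infusion if practicable and agreed by the subject. In contrast, "subjects in the follow-up period were to be discontinued as soon as possible".

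**The concern.** There are two separate problems.

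**Missing tables.** A thrombosis or haemolysis with onset in follow-up is never counted as an event of special interest. Thromboembolic events as defined in Protocol 9.3.7.1 include deep vein thrombosis, pulmonary embolism, myocardial infarction and cerebral infarction, so preferred-term rows scatter them across organ classes. A subject may have events in both windows, so adding the two windows' tables does not give the number of subjects affected over the trial.

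**Denominator.** A subject whose last contact falls within four weeks of the last infusion cannot have a post-treatment event as defined, yet is counted as event-free. At stake is the absolute late incidence, which a reader would take as the risk over a 24-week follow-up that some subjects did not have.

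**Working it through.** **Tables: the texts side by side**

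| Requirement | Protocol | SAP 11.1 |
|---|---|---|
| Treatment and follow-up TEAEs apart | yes (10.1.3) | yes |
| Both periods together | yes (10.1.3) | none listed |
| Thromboembolic and haemolytic events grouped | yes, no time limit (10.1.3) | on-treatment only |
| Departure declared | – | not in SAP 12 |

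The items overall and SAEs restart under each window, which fixes the window each item belongs to. The top-level TEAE line has no items of its own, so it does not read as a both-period table. SAP 4.2 lists AESIs as a safety variable without a time limit, so the restriction appears only in the table list.

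**Denominator: the windows**

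IV13 falls at Week 4 × (13 − 1) = 48. The post-treatment window opens at 48 + 4 = Week 52, and the final visit is at Week 76, so the window lasts 76 − 52 = 24 weeks. This reproduces the planned follow-up period. A subject whose final visit follows soon after IV13 has no time in this window.

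**Denominator: the dilution**

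Let r be the true 24-week post-treatment risk, f the share of the Safety population with cut follow-up, and g the weeks those subjects were observed after Week 52. The documents give none of the three, so all are assumed here. With a constant hazard λ = −ln(1 − r)/24:

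crude percentage = (1 − f) × r + f × (1 − exp(−λg))

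With g = 0 this is (1 − f) × r, a relative understatement of exactly f.

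| r | g (weeks) | f = 10% | f = 25% | f = 50% | f = 75% |
|---|---|---|---|---|---|
| 2% | 0 | 1.80% | 1.50% | 1.00% | 0.50% |
| 2% | 12 | 1.90% | 1.75% | 1.50% | 1.25% |
| 5% | 0 | 4.50% | 3.75% | 2.50% | 1.25% |
| 5% | 12 | 4.75% | 4.38% | 3.77% | 3.15% |
| 10% | 0 | 9.00% | 7.50% | 5.00% | 2.50% |
| 10% | 12 | 9.51% | 8.78% | 7.57% | 6.35% |

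With g = 12 the relative understatement is about 5%, 12%, 25% and 37%, nearly the same for each r.

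**Comparison between arms.** If the same fraction is cut in two arms with assumed risks of 5% and 2% and g = 0, then at f = 50% the difference falls from 3.0 to 2.5 − 1.0 = 1.5 points. The ratio stays at 2.5.

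**No events seen.** The one-sided 95% upper bound is 1 − 0.05^(1/n). For a planned arm of 42 it is 6.9%. If only 21 of them were observed, it is 13.3%.

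**The case against.** Late events are not hidden. They appear by preferred term in the post-treatment overall table, serious ones also in the SAE table, and all AEs are listed by treatment group and subject. The both-period total could be rebuilt by hand from those listings. This stands: the missing tables lose a grouped count and do not themselves understate risk.

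Structured thromboembolic and haemolysis monitoring runs only from IV1 to IV13 (Protocol 4.5.2.5 and 4.5.2.6), so the on-treatment tables roughly match active surveillance. That may explain the choice. However, AEs are collected at every follow-up contact, and Protocol 10.1.3 sets no such limit. The SAP revision history mentions a clarified breakdown of AE summaries, but it does not describe this restriction and does not replace an entry in SAP 12.

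On the denominator, Protocol 10.1.3 itself prescribes subject incidences and percentages, so the crude statistic is no departure from the protocol. The Safety denominator for the post-treatment rows is inferred from the general rule in SAP 11. SAP 6 will show completion of Weeks 52 and 76 by arm and stage, so the truncation will be visible. All of this stands, but no rule carries the disposition counts into the AE percentages.

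A reader might infer a bias between arms: Stage 2 contains only placebo and the selected dose, so truncation there would make the unselected dose look worse. The documents do not say that Stage 2 had opened, or how many subjects were cut in either stage. The termination was a business decision with treatment still blinded, which gives no reason to expect imbalance between concurrently randomised arms. A reader might also infer a continuing hazard after Week 52 from the IgG half-life in Protocol 2.4. That figure comes from 20 subjects with primary immunodeficiency at 0.3 to 0.6 g/kg and says nothing about event risk after dosing stops.

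**Conclusion.** The point holds in two limited parts.

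First, SAP 11.1 narrows the protocol's safety summaries without declaring it: no grouped special-interest count after last treatment plus 4 weeks, and no table over both periods. This follows from the texts and needs no assumption beyond the reading of the table list given above.

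Second, if the general Safety-population rule is followed, absolute post-treatment percentages are understated by f when the affected subjects have no observation in the window, and by less when they have some. The direction is clear. The size cannot be derived, because neither the number of subjects cut nor their remaining observation is stated. The percentages above are illustrations only. A distortion of the relative comparison between arms is not shown.

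This should be corrected before the tables are produced. It does not affect the efficacy analysis.

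**What to change.** In SAP 11.1:

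- Add tables of AESIs, suspected ADRs of special interest and ARs of special interest for post-treatment TEAEs, and a set of tables for all TEAEs over treatment plus follow-up.
- For post-treatment tables, use as denominator the Safety subjects observed beyond last treatment plus 4 weeks, and report subject-weeks observed with an exposure-adjusted rate. Both are needed: the restricted denominator removes subjects with no observation but still counts partly observed ones in full. Under the constant hazard used above, r = 5% corresponds to −ln(0.95)/24 = 0.00214 per week, or 0.214 per 100 subject-weeks, whatever f is, provided the cuts are unrelated to risk.
- Show these tables by stage as well as combined if Stage 2 has subjects.

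In SAP 12, declare any departure from Protocol 10.1.3 that is kept.

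The cost is SAP wording and a few extra tables from data already collected. The post-treatment percentages will look somewhat less favourable, and intervals based on the subjects actually observed will be wider.

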AEs temporally associated to the infusion of the investigational products (*i.e.*, infusional AEs, including infusional suspected ADRs), will be summarized by presenting infusion/subject incidences and percentage and ordered by ordinal number of infusions, and listed. In addition, the infusion rate in effect at the time of onset of the AE, the time the AE is first reported, and the time the AE changes materially in intensity and/or resolves will be also reported and listed. In addition, AEs temporally associated to the infusion of the investigational products for which the incidence in the Flebogamma[®] 5% DIF exceeds the incidence in the placebo group will be summarized separately.

Subjects with a serious adverse event (SAE) or who withdraw from the study because of an AE will also be individually listed and summarized.

AEs for which the investigator causality assessment is missing or undetermined will be individually listed.

Vital signs during infusions:

Vital signs (T, RR, HR, SBP and DBP) will be listed for each clinical trial subject. In case a subject presents a clinically relevant abnormality of vital signs (based on the Investigator's judgment) during an infusion, the event will be flagged and reported as an AE temporally associated to the infusion. All vital signs will be evaluated for each subject and for each infusion.

Physical assessment:

Physical findings (normal and abnormal) will be listed for each clinical trial subject. Any clinically relevant abnormality (based on the Investigator's judgment) developed by individual during the clinical trial and not already present at baseline will be reported as AE.

Blood biochemistry and cell counts:

All clinical laboratory data for renal (creatinine, BUN and GFR), hepatic (ALT, AST, ALP and TBL) and haematological parameters (CBC including differential leukocyte count) will be listed for each clinical trial subjects. Laboratory results out of the normal range judged by the Investigator as clinically relevant will be considered AEs.

	Number	GLB-PRT-FLB-IG1104	Version	7.0	Status	Effective	Effective Date	07-Mar-2022
CIVILOLS	IG1104 - A n	multicenter, prospective, randomized, placebo-controlled,	, double-blind	l, parallel-gro	up clinical trial	to assess the efficacy		70 F 3 - 00 F
Bioscience Industrial Group	and safety or	of Immune Globulin Intravenous (Human) Flebogamma®	5% DIF in pa	tients with P	ost-Polio Syndı	ome	rage	108 01 122

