12 CHANGES TO PROTOCOL SPECIFIED ANALYSES

12.1 Exploratory Analysis of Cytokine

In July 2022, Grifols decided to terminate the study early due as a business decision. For this reason, it was also decided that some of the IL-17 and IL23 testing would not be performed. As a result, these parameters will no longer be considered exploratory endpoints as originally planned, and available results for these parameters will be listed only.

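### SAP 11.1 omits, without declaring it, the protocol's per-infusion incidence and ordering by infusion number for infusional adverse events

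*SAP*

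**What the plan says.** Protocol 10.1.3 sets two levels of reporting. For adverse events in general the rule is at subject level: "All AEs will be summarized by presenting subject incidences and percentages". For infusional events, including infusional suspected ADRs, it asks for more: they "will be summarized by presenting infusion/subject incidences and percentage and ordered by ordinal number of infusions, and listed". It adds that infusional events whose incidence on Flebogamma "exceeds the incidence in the placebo group will be summarized separately". The protocol synopsis repeats this last requirement.

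SAP 11.1 defines infusional TEAEs with a window from the start of a two-day infusion period to 72 hours after the total dose is completed. Its AE tables are "summarized (stage 1 and stage 2 combined) by treatment group, system organ class (SOC) and preferred term (PT) as follows", and the infusional branch has three entries: overall, SAEs and suspected ADRs. One counting rule covers all of them: "Adverse events will be summarized by presenting, for each treatment group, the number and percentage of patients with any AE", and likewise within each SOC and PT. The section has no infusion denominator, no table by infusion number and no summary of events exceeding placebo.

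SAP 12 is the place for departures from the protocol's analyses. Its single entry is "12.1 Exploratory Analysis of Cytokine".

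**The concern.** SAP 2 says the SAP is based on protocol version 7.0, so the Protocol 10.1.3 rule is current. Protocol 10.1 leaves the detailed description of analyses to the SAP, so a table missing there will probably not be programmed. Protocol 10.5 says major deviations from the statistical plan will be documented in the SAP and study report, and nothing about this one is.

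Three things are at stake.

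- **Pattern over infusions.** Protocol 2.3 says people receiving IVIG for the first time may be at higher risk of fever, chills, nausea and vomiting. Exclusion criterion 1 bars immune globulin within the last 3 years, so the first study infusions are first or renewed exposures. A percentage of patients ever affected cannot separate the first infusion from later ones, whatever the event rate.
- **Exposure.** Protocol 7.1.1 allows up to 4 missed infusions, and subjects may withdraw. The chance of being counted at least once rises with the number of infusions received.
- **Contrast between arms.** For events that recur often, a measure of ever affected can shrink the risk ratio between arms.

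**Working it through.** **Inputs.** Infusions every 4 weeks for 52 weeks, each over two days (Protocol 7.1); at most 4 missed infusions before withdrawal is required (Protocol 7.1.1); 42 subjects per Stage 1 arm (Protocol 10.2). No infusional event rate appears in either document, so the per-visit risk p below is assumed and shown over a range.

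**Exposures.** 52/4 = 13 infusion visits and 13 × 2 = 26 infusions, as Protocol 7.1 states. The fewest visits without required withdrawal is 13 − 4 = 9. A per-infusion denominator would be up to 42 × 13 = 546 two-day periods per Stage 1 arm.

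**Ever affected, independent visits.** P = 1 − (1 − p)^13.

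| p per visit | Ever affected in 13 visits |
|---|---|
| 1% | 12.2% |
| 2% | 23.1% |
| 5% | 48.7% |
| 10% | 74.6% |
| 20% | 94.5% |
| 30% | 99.0% |

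Reaching 80% ever affected needs p = 1 − 0.20^(1/13) = 11.6%. Reaching 90% needs p = 1 − 0.10^(1/13) = 16.2%.

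**Dependence on exposure.** At p = 10%, 13 visits give 74.6% and 9 visits give 1 − 0.9^9 = 61.3%. The risk per infusion is the same; only the number of visits differs.

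**A true ratio of 2.0 between arms.** To allow for within-patient clustering, let p vary between patients by a beta distribution with intraclass correlation ρ. Then P = 1 − B(a, b + 13)/B(a, b), where B is the beta function, a = p(1/ρ − 1) and b = (1 − p)(1/ρ − 1).

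| Per visit | Independent | ρ = 0.3 |
|---|---|---|
| 1% v 2% | 12.2% v 23.1%, ratio 1.89 | 4.7% v 9.3%, ratio 1.96 |
| 5% v 10% | 48.7% v 74.6%, ratio 1.53 | 21.8% v 39.3%, ratio 1.80 |
| 10% v 20% | 74.6% v 94.5%, ratio 1.27 | 39.3% v 64.2%, ratio 1.63 |
| 20% v 40% | 94.5% v 99.9%, ratio 1.06 | 64.2% v 88.8%, ratio 1.38 |

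The shrinkage is large only when the event is common and clusters little within patients.

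**Absolute scale, independent visits.** For 5% v 10% the gap grows from 5 to 25.9 points. For 10% v 20% it grows from 10 to 19.9 points. For 20% v 30% it falls from 10 to 99.0 − 94.5 = 4.5 points.

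**The case against.** The patient count is one half of what Protocol 10.1.3 asks for, and the SAP keeps it. The synopsis is softer on infusional events, asking only that they be summarised and listed. SAP 11.1 lists all AEs, SAP 5 lists all eCRF data, and SAP 9.3 summarises the number of infusions received. The summary of events exceeding placebo can largely be read off the planned patient table by arm and preferred term, since the protocol does not say which incidence it uses. The dose-selection rule in SAP 5.4 runs on 2MWD, subject to no safety concern, and the documents do not say that these tables inform that judgement.

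Most of this stands and limits the consequence, but it does not remove the gap. A listing by treatment group and subject gives no rates, denominators or order by infusion. An exposure summary not linked to events does not adjust for exposure. Nothing in the planned tables yields infusion-level incidence.

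A reader might go further and infer that over 13 infusions the patient measure saturates near 100% in every arm and so hides dose differences. The documents do not support that. They state no infusional event rate. All subjects are pre-medicated to reduce infusion reactions, and the infusion rate is titrated (Protocol 4.4.4.3). Saturation needs a common event with little clustering. Individual preferred terms and SAEs will usually be much rarer than any infusional event, and for rare events the ratio is nearly preserved. At moderate rates the absolute gap between arms widens.

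**Conclusion.** The point holds as an undeclared departure from the protocol's safety analysis. It goes beyond missing detail: followed as written, SAP 11.1 replaces an analysis per infusion and per subject with one per subject only. This part rests on the text alone and needs no assumption about rates, and neither does the loss of the pattern over infusion number.

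The dependence on exposure and the compression of risk ratios have no documented size, because every rate above is assumed. Compression ranges from slight (1.89 for 1% v 2%) to marked (1.27 for 10% v 20%) if visits are independent, and it is weaker with clustering (1.63 for 10% v 20% at ρ = 0.3). It is a possibility for common infusional events and not a general property of the planned tables. The primary efficacy analysis is unaffected.

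**What to change.** Add to SAP 11.1, alongside the patient-level tables, descriptive tables of infusional TEAEs and infusional suspected ADRs per infusion given, by arm and by infusion number. Restore the separate summary of infusional events more frequent on Flebogamma than on placebo, and say which incidence it uses.

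State whether the denominator is the 13 two-day infusion periods or the 26 single infusions. The SAP's infusional window covers the whole two-day period, so the period matches it directly. Single infusions would need a rule for assigning an event to a day, and in the 1 g/kg arm one of the two days is saline (Protocol 4.4.2.3). A visit with only Day 1 given is not a missed infusion under Protocol 7.1.1, so its place in the denominator should be stated too.

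If intervals are shown, they should allow for within-subject clustering. That is optional and goes beyond the protocol's descriptive safety plan. If the sponsor prefers to leave the tables out, the omission should be declared and justified in SAP 12.

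The cost is two or three extra tables. AE onset date and time and infusions received are already collected.
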